4.3 Study Population

The study population will be screened at the respiratory institute of Soroka University Medical Center and will include patients who are referred for pulmonary function tests (PFTs) for any reason. The study population will be enrolled according to the following inclusion and exclusion criteria.

4.3.1 Inclusion Criteria-

- Age 18 or above
- Referral for full pulmonary function tests (PFTs)
- Patients are willing and able to sign the informed consent form.

4.3.2 Exclusion Criteria

- Unable to give written informed consent.
- Unable to remain supine.

- Poor effort at PFTs
- Subcutaneous emphysema

4.3.3 Withdrawal Criteria

Participants who are unable or unwilling to complete the study procedures during their pulmonary institute visit or withdraw their consent for the researcher to access their electrical medical record and case report form within the following year after participation will be withdrawn from the study. Nevertheless, the results collected until the point of withdrawal will still be included in the study results as appropriate.

4.4 Enrollment

Before participating in this study, the Investigator must obtain written approvals from the ethics committee and other local regulatory bodies as appropriate approval for the protocol and the informed consent form. Failure to obtain a signed and hand-dated informed consent before the procedure constitutes a protocol violation, which is reportable to the EC.

4.5 Patient Screening

The screening will be performed at the respiratory institute of Soroka University Medical Center and will include patients who are sent for pulmonary function tests (PFTs) for any reason.

Soroka university medical center is a 1,000-bed university-affiliated referral center in Southern Israel, directly serving a population of over 700,000 and serving as a tertiary hospital for nearly 1 million people.

Patients who are sent for pulmonary function tests (PFTs) for any reason and fulfill all the inclusions and none of the exclusion criteria will be approached and offered participation by a study research member. A study research member will explain the study's purpose, procedures, and intent to each potential participant. Interested patients will be asked to provide written consent before performing any study procedure.

4.6 Study Procedures

The study will be performed in a fully paired fashion, i.e., a direct comparison in which all study participants receive the index test (sonographic assessment) and the reference standard (PFTs).

This should enhance the resulting precision relative to the number of study participants. The three following steps are planned to take place at the same visit:

1. Enrollment, including obtaining written informed consent.
2. PFTs, performed as planned.
3. A sonographic evaluation comprised of both lung and cardiac POCUS scans, performed by an experienced sonographer, blinded to the patient's medical history or PFTs results.

Steps two and three can be replaced in order as long as the POCUS operator is blinded to the PFTs results. The PFT technician is not part of the study team and will be blinded to the POCUS findings as well.

4.7 Study Duration

The evaluation is estimated to be around 10 minutes from the initial consent and will not interfere with the purpose of the patient's visit. We will collect the sonographic data prospectively based on the POCUS examination performed, while additional medical data will be collected retrospectively from the medical records (as specified below). We expect enrollment in the study to last for approximately twelve months.

4.8 Data to Capture

4.8.1 Required Data

We aim to collect the sonographic data as well as the PFT results for each participant. Furthermore, we plan to gather descriptive data from the medical records including –

1. Age -continuous variable. Values: above 18.
2. Gender - dichotomic variable (Female=1, Male=0).
3. BMI - continuous variable.
4. Smoking history (pack years)- continuous variable.
5. Comorbidities - nominal variable. Values: dichotomic variable (Yes=1, No=0)
6. Hypertension – ordinal variable. (0=Normal, 1=Elevated, 2= Stage 1, 3 = Stage 2, 4= Hypersensitive crisis). Values: 0=systolic<120 & diastolic<80, 1=systolic=120-129 & diastolic<80, 2=systolic=130-139 & diastolic 80-89, 3=systolic>140 & diastolic>90, 4= systolic>180 & diastolic>110.
7. Diabetes - dichotomic variable (Yes=1, No=0)
8. Other Lung diseases (such as cystic fibrosis, bronchiectasis, Interstitial lung disease, etc) - dichotomic variable (Yes=1, NO=0)
9. Ischemic Heart Disease - dichotomic variable (Yes=1, No=0)
10. Degree of dyspnea (based on the mMRC Dyspnea Scale) - ordinal variable (1=Grade 1 ,2= Grade 2, 3=Grade 3, 4 =Grade 4). See supplements for mMRC dyspnea scaling system.
11. Hemoglobin level (g%) - continuous variable.
12. Latest Venous/Arterial pH- continuous variable.
13. Latest Venous/Arterial HCO3- - continuous variable.
14. Latest Venous/Arterial pCO2- continuous variable.
15. Latest Arterial pO2 - continuous variable.
 - a. The blood attributes under investigation will be derived retrospectively from the electronic medical record of the current hospitalization, and blood tests will not be performed as part of this trial.
16. Past computed tomographic scans (most recent and up to 5 years prior) - ordinal variable (0= no emphysema (score 0),1= \leq 25% emphysema (score 1),2= \leq 50% emphysema (score 2), 3= \leq 75% emphysema (score 3),4= $>$ 75% emphysema (score 4)).

All required data for this study will be collected via electronic case report forms (eCRF).

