4.2.2 Secondary Objective

- To estimate the association between the sonographic score and the most recent (<5 years) computed tomography (CT) scan score (i.e., emphysema score).
- To estimate the association between the sonographic score and the patient's subjective severity of dyspnea (estimated by the mMRC scale).
- To estimate the association between the sonographic score and the patient's diffusion lung capacity (DLCO).
- To determine the sonographic components that are the most sensitive for the diagnosis of COPD.
- To assess the additive value of the patient's smoking status to the diagnostic accuracy of the sonographic score.

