4.8.2 Data Collection

The final set of CRFs is designed to accommodate the specific features of the trial design. Modification of CRFs will only be made if deemed necessary by Soroka CRC. The CRFs will be filled out manually by the study personnel and or will be collected through the computer services database.

[figure not shown]
The following data will be collected:

- Demographic data: Age, Gender, BMI
- Detailed medical history, including smoking history, comorbidities, degree of dyspnea reported (based on mMRC score), and recent computed tomographic scan (up to 5 years prior).
- PFT results
- POCUS exam results

5 Statistical Considerations and Analysis Plan

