8.1 Sources of Materials

No tissue or any other physical specimen will be taken from the patients.

All of the data obtained for this study will be obtained prospectively.

Copies of data obtained as part of the study will be retained by the clinical research center, with appropriate source documentation, on all subjects that sign informed consent. The data utilized in this study are described above and consist of information from medical records or study-specified measures and interventions.

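### The mMRC grade for the dyspnoea objective is taken from medical records with no date limit, and no visit step asks about dyspnoea, so its age and completeness are uncontrolled

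*Combined protocol and SAP*

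**What the plan says.** - **Objective.** Section 4.2.2 sets out: "To estimate the association between the sonographic score and the patient's subjective severity of dyspnea (estimated by the mMRC scale". Section 5.2 analyses this with a Mann-Whitney U test and gives no rule for a missing or old grade.
- **Source.** Section 4.7 separates the prospectively collected ultrasound data from the rest: "additional medical data will be collected retrospectively from the medical records (as specified below". Section 4.8.1 is the specification it points to. The list there opens with "Furthermore, we plan to gather descriptive data from the medical records including", and item 10 reads "Degree of dyspnea (based on the mMRC Dyspnea Scale) - ordinal variable", with no date or look-back limit.
- **Visit.** Section 4.6 states "The three following steps are planned to take place at the same visit" and then lists consent, PFTs and the ultrasound scan. None of these elicits dyspnoea.
- **Other descriptions.** Section 4.8.2 puts dyspnoea under medical history: "degree of dyspnea reported (based on mMRC score), and recent computed tomographic scan (up to 5 years prior". The five-year limit there belongs to the CT scan. Section 8.1 says: "All of the data obtained for this study will be obtained prospectively".

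**The concern.** Dyspnoea is reported by the patient and can change over time and with treatment. The scan and the PFTs are planned for one visit, but the stated source of the grade is a chart entry that could come from any date. If several entries exist, nothing says which to use. If none exists, the patient has no value for this analysis.

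Two things are at stake, both confined to this objective. Mistimed grades add misclassification, which weakens a rank association when the errors are unrelated to the score. Missing grades reduce the number analysed, and the plan does not ask for that number to be reported.

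**Working it through.** The plan states no figure on this point, so the first step is to compare the text and the second is an illustration under assumptions.

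**1. Time anchors in section 4.8.1**

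| Record item | Time anchor |
|---|---|
| CT emphysema score | most recent, up to 5 years back |
| Blood gases | latest value |
| Blood results generally | current hospitalization |
| mMRC grade (item 10) | none |

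Other record-derived items that vary over time were anchored. The mMRC grade, which carries its own objective, was not.

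**2. Do the other sections supply a visit grade?** Section 4.6 has no such step. Section 4.8.2 gives no date and lets the CRF be completed by hand or from a database, which describes data entry and does not show that the patient was asked. Section 8.1 cannot be literally true alongside 4.7 and 4.8.1, because past CT scans and earlier blood results are retrospective by nature, and it names no mMRC step. The sections conflict, and the two that are specific about source point to the chart.

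**3. Size of attenuation (all inputs assumed).** mMRC grades 0 to 4 in proportions 20/30/25/15/10%; a bivariate normal pair cut into a 0–10 score and five grades; 400,000 simulated patients; 25% or 50% of grades moved one step at random.

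| Grades moved | Spearman correlation | Loss |
|---|---|---|
| 0% | 0.369 | – |
| 25% | 0.343 | 1 − 0.343/0.369 = 7% |
| 50% | 0.318 | 1 − 0.318/0.369 = 14% |

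A repeat run agreed with these values when a move off either end of the scale left the grade unchanged. Half of the moves among the 30% of patients in the end grades are then void, so the share actually wrong is 0.85 × 25% = 21% and 0.85 × 50% = 43%.

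**4. What that does to power.** Approximate power = Φ(atanh(ρ) × √((n − 3)/1.06) − 1.96), two-sided α = 0.05, with n = 200 from section 5.1.

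- ρ = 0.369, n = 200: 0.387 × 13.63 = 5.28; 5.28 − 1.96 = 3.32; power above 99.9%.
- ρ = 0.318, n = 200: 0.329 × 13.63 = 4.49; 4.49 − 1.96 = 2.53; power 99.4%.
- ρ = 0.318, n = 100 (half the grades missing): 0.329 × 9.57 = 3.15; 3.15 − 1.96 = 1.19; power 88%.

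**5. Weaker true correlations (also assumed).** The same formula gives:

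| True ρ | n = 200 | n = 100 | ρ cut to 60%, n = 200 | Both |
|---|---|---|---|---|
| 0.30 | 98.8% | 84.2% | 69.9% | 41.3% |
| 0.20 | 78.9% | 49.2% | 37.6% | 21.0% |

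The last two columns assume a 40% loss of correlation, about three times the largest loss in step 3 (40/14 = 2.9). The first two show that missing grades alone can matter if the true association is weak.

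Steps 3 to 5 use a rank correlation, whereas the plan names a Mann-Whitney test with no stated grouping. They indicate scale and do not reproduce the planned analysis.

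**The case against.** The strongest defence is that the documents leave room for a same-day grade. Section 4.8.2 speaks of reported dyspnoea and allows staff to complete the CRF by hand, the supplement prints the scale in first-person wording, and section 8.1 calls all data prospective. A grade charted on the day of the PFTs would also be contemporaneous. This stands as a limit: mistiming is a risk that the text permits and is not an established fact. It does not remove the gap, because nothing requires a same-day grade.

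Three stronger readings are tempting but not supported:

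- **That a null result could not be told apart from stale data.** In the scenario of step 3, power at 200 patients stays at about 99%, so random one-step errors would rarely produce a null. The low power figures need a weaker true correlation, heavy missingness or a much larger attenuation, and the documents establish none of these.
- **That grades are more often charted in patients already followed for lung disease, so the analysed subset is selected on disease.** This is conceivable, but the documents say nothing about who has a charted grade.
- **That the association must be biased towards zero.** That follows only if the errors are unrelated to the score. The Design section helps here, since a third party blinded to the ultrasound extracts the record data, but blinding does not make an old grade current.

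It can also be said that naming the source and a maximum interval between grade and scan would suffice. That would settle the dating, but it would still lose every patient with no charted grade inside the interval.

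**Conclusion.** The point holds as a weakness in data source and timing for one of five secondary objectives. As sections 4.7 and 4.8.1 are written, the grade is an undated chart entry; section 4.6 provides no alternative, and sections 4.8.2 and 8.1 leave the source unclear or contradict it.

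The likely effect is some attenuation, about 7 to 14% of the rank correlation under the assumed grade mix and error rates, plus an unknown amount of missing data. The primary sensitivity, specificity and AUC analyses do not use the grade and are untouched. The textual gap is certain; its consequence in practice depends on how current and complete the charts are, which the documents do not show. The change is worth making because it is cheap and a same-day grade cannot be recovered once the visit is over.

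**What to change.** - **Section 4.6, step 1.** The research member who takes consent, not the blinded ultrasound operator, asks the patient to choose an mMRC grade from the supplement scale and enters it in the eCRF. The operator is not told the grade.
- **Section 4.8.1.** Move item 10 from record-derived data to data collected at the visit. Item 10 currently codes grades 1 to 4 while the supplement runs from 0 to 4, so the eCRF field must also accept grade 0.
- **Sections 4.7, 4.8.1, 4.8.2 and 8.1.** Reconcile them so that each variable has one stated source and timing.
- **Section 5.2.** Use the visit grade for the dyspnoea analysis, flag record-derived grades from patients enrolled earlier, and report the number of usable grades.

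The cost is a short amendment and about a minute per patient at a contact that already takes place, with no extra staff. The downside is a mixed source for patients already enrolled. The change does not settle how a two-group test is to be applied to a scale with several grades and no stated cut; that is a separate point.

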4.8.2 Data Collection

The final set of CRFs is designed to accommodate the specific features of the trial design. Modification of CRFs will only be made if deemed necessary by Soroka CRC. The CRFs will be filled out manually by the study personnel and or will be collected through the computer services database.

[figure not shown]
The following data will be collected:

- Demographic data: Age, Gender, BMI
- Detailed medical history, including smoking history, comorbidities, degree of dyspnea reported (based on mMRC score), and recent computed tomographic scan (up to 5 years prior).
- PFT results
- POCUS exam results

5 Statistical Considerations and Analysis Plan

5.1 Sample Size Considerations

In this study, the sample size calculation was aimed to ensure an accurate estimate of sensitivity (Se) and specificity (Sp) of the POCUS examination vs the gold standard PFTs. We aim to enroll a total of 200 patients. The calculation stems from the speculation that the Se of the test will be 85%, with a confidence interval of 90% and the maximal width of the interval will be up to $\pm 7\%$.

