**Diagnosing Obstructive Lung Disease with Point of Care Ultrasound-
A Cross-sectional, Diagnostic Accuracy Test**

Clinical Research Center, The Medical Intensive Care Unit, and Pulmonary Institute
Soroka University Medical Center,
Be'er-Sheva, Israel

Protocol SCRC23032

Version 1.2

September 2023

1 Investigator Signature Page

Study Title: Diagnosing Obstructive Lung Disease with Point of Care Ultrasound, A Cross-sectional, Diagnostic accuracy test

Protocol Version: Version 1.1

Protocol Date: 18 June 2023

Investigator's Responsibility

Prior to participation in the study, as the site principal investigator, I understand that I must obtain written approval from my local Ethics Committee (EC) and the hospital General Director.

As the site Principal Investigator, I must also:

1. Ensure that the study is not commenced until EC and hospital General Director approvals have been obtained.
2. Ensure that written informed consent is obtained from each patient prior to any data collection using the most recent EC-approved Patient Informed Consent Form.
3. Provide all required data and reports and agree to source document verification of study data with the patient's medical records.
4. Allow EC representatives, to inspect and copy any documents pertaining to this clinical investigation.

Investigator Signature

I have read and understand the contents of the study protocol and agree to abide by the requirements set forth in this document.

[name]

Investigator Name (print)

Soroka University Medical Center

Investigative Site (print)

[name]

Investigator Signature

June 18, 2023

Date

2 Protocol Summary

OBJECTIVE	To assess the accuracy of the Point of Care Ultrasound (POCUS) exam in diagnosing obstructive lung diseases (OLDs) compared to the gold standard pulmonary function test (PFTs)
STUDY DESIGN	A cross-sectional diagnostic accuracy test
INTERVENTION	None
SAMPLE SIZE CONSIDERATIONS	We aim to enroll a total of 200 patients. The calculation stems from the speculation that the Se of the test will be 85%, with a confidence interval of 90% and the maximal width of the interval will be up to $\pm 7\%$.
INCLUSION CRITERIA	
• Age 18 or above• Referral for full pulmonary function tests (PFTs)• Patients are willing and able to sign a written informed consent form.
EXCLUSION CRITERIA	
• Unable to give written informed consent.• Unable to remain supine.• Poor effort at PFTs• Subcutaneous emphysema

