5.2 Statistical Analyses

Data collected in this study will be documented using summary tables. Descriptive statistics will be provided. The statistics for continuous variables will include mean, standard deviation, minimum, maximum, and sample. Categorical variables will be described with numbers and percentages. Comparisons between the groups will be presented with Differences (with 95% Confidence Intervals) and/or P-values. Percentages will be rounded to one decimal place.

Primary Objective Analyses

To evaluate the diagnostic accuracy of the "sonographic COPD score" for COPD diagnosis, we will calculate sensitivity, specificity, positive predictive value (PPV), and negative predictive value (NPV). We will then construct a Receiver Operating Characteristic (ROC) curve based on the sensitivity and specificity values to evaluate the performance of the POCUS score compared to the gold standard test, the pulmonary function test. The area under the ROC curve (AUC) will be calculated to assess the accuracy of the POCUS score in diagnosing COPD. Performances are evaluated at two different operation points: the first one is at 80% of sensitivity, and the other is at knee-point, which represents the best point reached by the ROC curve, close to the upper left bond. The presence of obstructive lung disease (OLD) detected by both ultrasound and PFTs will be labeled as true positive, the presence of OLD detected only by ultrasound and not by PFTs will be labeled as a false positive, no OLD detected by both ultrasound and PFTs will be labeled as true negative, and the presence of OLD detected by PFTs and not by ultrasound will be labeled as a false negative.

Secondary Objective Analyses

- To estimate the association between the sonographic score and the most recent (<5 years) computed tomography (CT) scan score (i.e., emphysema score) - we will use a Spearman's rank correlation coefficient.
- To estimate the association between the sonographic score and the patient's subjective severity of dyspnea (estimated by the mMRC scale)- we will use the Mann-Whitney U test to determine the association between the sonographic score and the mMRC scale.
- To estimate the association between the sonographic score and the patient's diffusion lung capacity (DLCO) - We will use the Mann-Whitney U test to determine the association between the sonographic score and DLCO.

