- To determine the sonographic components that are the most sensitive for the diagnosis of OLD - we can use a logistic regression analysis. The regression will provide estimates of the effect of each sonographic component on the probability of being diagnosed with OLD. In this analysis, we can use the sonographic components as predictor variables and OLD diagnosis as the outcome variable.
- To assess the additive value of the patient's smoking status to the sonographic score's diagnostic accuracy- will be based on a logistic regression analysis. In this analysis, we can use the sonographic score and smoking status as predictor variables and OLD diagnosis as

the outcome variable. The regression will provide estimates of the effect of each predictor on the probability of being diagnosed with OLD, as well as an estimate of the additional effect of smoking status beyond the sonographic score.

All statistical tests and/or confidence intervals, as appropriate, will be performed at $\alpha=0.05$ (2-sided) or $\alpha=0.025$ (1-sided), except for those specified otherwise. All p-values reported will be rounded to three decimal places. All statistical analyses will be conducted using SPSS 29.0 statistical software (IBM Corp Armonk, NY, USA).

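### Does the missing OLD proportion behind N=200 undermine the planned ±7% precision for sensitivity?

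*Combined protocol and SAP*

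**What the plan says.** Section 5.1 states the purpose of the sizing: "the sample size calculation was aimed to ensure an accurate estimate of sensitivity (Se) and specificity (Sp) of the POCUS examination" against PFTs. It then gives the total, "We aim to enroll a total of 200 patients", and the basis: "The calculation stems from the speculation that the Se of the test will be 85%, with a confidence interval of 90" per cent, with a maximal half-width of 7 percentage points. The Protocol Summary repeats the total and the basis. Neither place gives an expected OLD proportion, a required number of OLD patients or an expected specificity.

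Section 4.3 says the population "will include patients who are referred for pulmonary function tests (PFTs) for any reason", so the 200 will be a mixture of patients with and without OLD.

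Section 5.2 sets the general level: "All statistical tests and/or confidence intervals, as appropriate, will be performed at" two-sided alpha 0.05 (or one-sided 0.025), "except for those specified otherwise". The one place where 5.2 writes 95% explicitly concerns group contrasts: "Comparisons between the groups will be presented with Differences (with 95% Confidence Intervals) and/or P-values". For the ROC analysis it adds: "Performances are evaluated at two different operation points: the first one is at 80% of sensitivity", the other being the knee of the curve.

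**The concern.** By the definitions in 5.2, the denominator of sensitivity is true positives plus false negatives, that is, PFT-positive patients only. A precision statement for sensitivity fixes the number of OLD patients. It becomes a total only after division by the expected OLD proportion, and that number is absent. If few referrals have OLD, the sensitivity interval will be wider than the text suggests.

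Two further points add to the unease. The sizing uses 90% while the general level in 5.2 corresponds to 95%, so the reported interval might be wider than the planned one for that reason alone. Specificity is named as a target of the calculation but has no planning value. Precision is the only justification offered for 200, so if it failed, the sample size would have no stated basis.

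**Working it through.** **Inputs from 5.1:** Se = 0.85, half-width d = 0.07, 90% interval (z = 1.645), N = 200. For the level in 5.2, z = 1.960. The documents name no interval method; Wald is used here. All OLD proportions and specificities below are assumptions, because the documents give none.

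**Step 1. OLD patients required.** n = z² × Se × (1 − Se) / d²

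- 90%: 1.645² × 0.1275 / 0.0049 = 70.4. With 70 patients the half-width is 7.02 points; with 71 it is 6.97.
- 95%: 1.960² × 0.1275 / 0.0049 = 99.96, so 100.

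**Step 2. Can 200 be reproduced?** Not from the stated inputs alone. If all 200 were the denominator, the 90% half-width would be ±4.2 points, so 200 was not meant as the OLD count. With an OLD proportion of 35%, 70.4 / 0.35 = 201. Working back from exactly 71, 71 / 200 = 35.5%. The stated figures therefore fit together at the stated 90% level if about 35% of referrals have OLD. At 95% they would need 100 / 200 = 50%.

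**Step 3. Sensitivity to the unstated proportion.** Half-width = z × √(0.1275 / n), with N = 200:

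| Assumed OLD proportion | OLD patients | 90% half-width | 95% half-width |
|---|---|---|---|
| 25% | 50 | ±8.3 | ±9.9 |
| 30% | 60 | ±7.6 | ±9.0 |
| 35% | 70 | ±7.0 | ±8.4 |
| 40% | 80 | ±6.6 | ±7.8 |
| 50% | 100 | ±5.9 | ±7.0 |

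At the 90% level the departure from ±7 is at most 8.3 − 7.0 = 1.3 points over this range.

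**Step 4. Chance of reaching 71 OLD patients**, binomial with N = 200: 5% if the true proportion is 30%, 47% at 35%, 92% at 40%.

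**Step 5. Specificity.** Half-width = z × √(Sp × (1 − Sp) / non-OLD count). At an assumed Sp of 80%, the 90% / 95% values are ±5.6 / ±6.6 with 140 non-OLD patients (30% OLD), ±5.8 / ±6.9 with 130 (35%), ±6.0 / ±7.2 with 120 (40%) and ±6.6 / ±7.8 with 100 (50%). At 90% all of these lie inside 7 points.

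**Step 6. Interval method.** Wilson gives the same 71 and 100. Clopper-Pearson, judged by average half-width, needs 83 OLD patients (41.5% of 200) at 90% and 113 (56.5%) at 95%. The value of about 70 therefore belongs to Wald or Wilson and is not a sharp threshold.

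**The case for a change.** The strongest case for a change is that ±7% is written as a maximum and is the sole support for 200, yet a reader cannot verify it. If only 30% of referrals have OLD, the target is very probably missed (5% chance of 71 or more). An analyst who takes the level in 5.2 literally will report ±8.4 points where 5.1 led the reader to expect ±7.0. Supplying the missing inputs would take a few sentences.

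Part of this stands. The OLD proportion and the expected specificity are not reported, and the interval level for sensitivity and specificity could have been stated once and unambiguously.

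The rest does not carry the point further. The 5.1 text presents its inputs as speculation and 200 as an aim, so ±7 reads as a planning value, not a guarantee. The exception clause in 5.2 does not require exceptions to be listed in that section, and 90% is specified in both 5.1 and the Protocol Summary. It is fair to reply that 5.1 describes sizing and not analysis, but that leaves an ambiguity and not a contradiction. Either level gives a valid interval around the same estimate, and the level is visible once the interval is labelled.

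The 80%-sensitivity operating point might seem to make specificity the only uncertain quantity there, and so make its missing planning value more serious. That goes too far. The score takes only 11 values (0 to 10), so a cut-off will seldom give exactly 80%, and the cut-off is chosen from the same data. Sensitivity remains uncertain at that point too, and a simple binomial half-width for specificity could understate its uncertainty.

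**Conclusion.** No change to the plan follows. Section 5.1 leaves out a planning input, but no stated figure is shown to be wrong: 85%, a 90% interval, ±7 points and 200 patients agree if about 35% of referrals have OLD and a Wald or Wilson interval is used. Whether the sponsor assumed that proportion cannot be known from the documents.

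Writing the input down would leave the sample size, recruitment and analyses as they are. No success criterion is tied to ±7 points. The OLD count is set by who is referred, and the published intervals will be computed from the patients observed, so any shortfall will show in their width. For assumed OLD proportions of 25% to 50%, the 90% half-width for sensitivity runs from ±8.3 to ±5.9 points. Reading the level as 95% widens an interval by a factor of 1.960 / 1.645 = 1.19, for example from ±7.0 to ±8.4 with 70 OLD patients. These figures assume a true sensitivity of 85%. The gap is one that analysts can fill sensibly when they report the OLD and non-OLD counts and label the confidence level.
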